# 1 SYNOPSIS

**TITLE: Food Allergen Elimination and a Brief, Therapeutic Exercise for Obesity Reduction**

**OBJECTIVES:**

Primary: The purpose of this study was to determine if removing food allergens alone or combined with a multi-discipline weight loss protocols are effective in obesity reduction.

NAME OF COMPANY: Galveston Clinical Research Foundation

STUDY SITES: Galveston, Texas, USA

METHODOLOGY: Randomized, Controlled, Cross-over Trial

NUMBER of PATIENTS: 18

Inclusion:

- 1) Healthy adults, ages 20 – 75
- 2) Body Mass Index  $\geq 30$

Exclusion:

- 1) Cardiovascular Heart Disease
- 2) Hypothyroid Secretion (Can reapply after Treatment and normal TSH, T3, T4 levels)
- 3) Hypogonadal syndrome (Can reapply after Treatment and normal testosterone levels.)
- 4) CVA, TBI or any neural injury or disease
- 5) Diabetes Mellitus (Type I or II)
- 6) Other weight loss protocols, diets, or medication (30 day wash out)

Randomized Categorization

- N/A

STATISTICAL METHODS:

A Repeated Measures ANOVA will measure changes in weight, body composition, and BMI.

SAFETY:

Serious Adverse Events associated with study procedures (ALCAT Blood draw, dietary changes and 2-minute exercise sessions) will be reported to the IRB within 24 hours and to the FDA as required by IRB.

**2.**

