##### **5.2.1.2 Premature Patient Discontinuation from the Study**

Patients are free to withdraw consent and/or discontinue participation in the study at any time, without prejudice to further treatment. A patient's participation in the study may also be discontinued at any time at the discretion of the Principle Investigator or Primary Care Physician.

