## **8. STUDY ASSESSMENTS**

### **8.1 Study Schedule of Events**

A screening phone call will evaluate the following:

- Eligibility (BMI, age, etc.)
- Medication eliminations (i.e. insulin, propranolol, etc.)

The initial meeting at the clinic will include the following:

- Informed consent and description of the study
- Confirmation of study eligibility
- Review of full medical history

Meeting for Enrolment will include the following:

- Consultation with PI
- Collection of blood through venipuncture for Food Allergen testing
- Demonstration of Aerobic-surge protocol and testing that subject understands
- Physical Examination
- Enrolment
- Initial Body Composition Testing.

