## **9 ADVERSE EVENT REPORTING**

### **9.1 Adverse Event**

For the purpose of this protocol, the following definitions and reporting requirements will apply:

An adverse event (AE) is any untoward medical occurrence associated with the performance of a study procedure in a clinical investigation patient.

AEs may include:

- Symptoms described by the patient
- Clinically significant changes in the patient's physical exam or other signs observed by the Investigator or medical staff

Definition of a Procedure-related AE:

A procedure-related AE is an AE occurring during a clinical study that is considered by the Investigator or the Medical Monitor (or designee) to be related to a research procedure (i.e., related to the fact that a patient is undergoing a procedure in the study). For example, a procedure-related AE may be an event related to a medical procedure required by the protocol (a single blood draw or an injury from an Aerobic-surge performed in the normal course of this study).

Only serious procedure-related adverse events will be recorded.

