### **11.3 Analysis Sets**

All study patients for whom data are available will be included in the analysis dataset. All study patients who complete the 30-day assessments will be included in the safety dataset.

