### **11.4 Demographics and Baseline Characteristics**

Demographic and baseline characteristics (age/age categories, sex, race, ethnicity, and baseline characteristics) will be analyzed using the safety analysis set. Summary statistics (n, mean, median, standard deviation, minimum, and maximum) will be reported. Information collected from the targeted medical history will be summarized in the same fashion as the other baseline characteristics.

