### **11.8.1 Physical Examination and Vital Signs**

Physical Examination will be performed as a screening method to exclude cardiovascular pathologies such as arrhythmia or history of myocardial infarction before initiation of the subject's participation in this study.

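### The safety set depends on completing 30-day assessments that the schedule does not contain, and the baseline table is built on it, so exposed subjects who leave before day 30 drop out of both

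*Protocol*

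**What the plan says.** Protocol 11.3 defines two sets. For the analysis dataset: "All study patients for whom data are available will be included in the analysis dataset". For the safety dataset: "All study patients who complete the 30-day assessments will be included in the safety dataset". Section 11.4 then says that demographic and baseline characteristics "will be analyzed using the safety analysis set".

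The safety paragraph of the synopsis shows what counts as exposure: "Serious Adverse Events associated with study procedures (ALCAT Blood draw, dietary changes and 2-minute exercise sessions" (the bracket closes after these words). Section 9.1 gives as examples of a procedure-related event "a single blood draw or an injury from an Aerobic-surge performed in the normal course of this study". Section 8.1 places the blood draw at the enrolment meeting: "Collection of blood through venipuncture for Food Allergen testing". Section 8.1 covers a screening call, an initial meeting and the enrolment meeting, and lists nothing later.

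On leaving the study, 5.2.1.2 says: "Patients are free to withdraw consent and/or discontinue participation in the study at any time". Participation lasts 90 days (5.2.1, 5.2.1.1, 5.2.1.3). Day 30 otherwise appears on study only as the end of daily texting (5.2.1.1). The synopsis also has a 30-day wash-out, which precedes the study.

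On SAEs, 9.4.1 requires related or possibly related events to be reported to the IRB within 24 hours, and 11.8 lists any such event. Section 11.8.3 says that only those related to invasive procedures are recorded.

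**The concern.** A safety population should hold everyone who was exposed, because people who tolerate a procedure poorly may be among the first to leave. Here entry depends on staying in the study, and on an assessment that the protocol never schedules. As written, nobody can say exactly who qualifies.

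The condition carries over to the baseline table. Under 7.2 subjects volunteer for the added PAN-5 programme, and 7.3 rules out randomization (the synopsis and the risk summary call the trial randomized, which is a separate contradiction). With self-selected groups, the baseline table is a main means of judging whether they were comparable at the start. Restricting it by something that happens after baseline hides how early leavers differed. It may also fail to describe the subjects in the analysis dataset.

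**Working it through.** The plan gives no figure to reproduce. The check follows one subject through the sections and then sizes the omission.

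**Tracing a subject who gives blood, begins the diet or exercise, and leaves before day 30**

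| Output | Governing section | Is the subject in it? |
|---|---|---|
| Analysis dataset | 11.3, available data | Possibly: no 30-day condition, and initial body composition is measured at enrolment (8.1) |
| Safety set | 11.3, 30-day assessments complete | No |
| Demographic and baseline table | 11.4, uses the safety set | No |
| SAE report to the IRB | 9.4.1 | Yes, if related or possibly related |
| SAE listing | 11.8 | Yes, if related or possibly related |
| SAE recording | 11.8.3 | Only if linked to an invasive procedure |

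The safety set can therefore be smaller than the analysis dataset. A listed SAE could belong to a subject who is in neither the safety set nor the baseline table.

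**Would scheduling a 30-day visit be enough?** No. The visit would make the condition determinable, but the subject above would still fail it.

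**Size of one omission.** Inputs: N = 18 (synopsis) or N = 20 (11.2). Share lost = 1/N.
- N = 18: 1/18 = 5.6%, leaving 17/18 = 94.4%.
- N = 20: 1/20 = 5.0%, leaving 19/20 = 95.0%.

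**Effect on a baseline percentage (illustration).** Assume that half the subjects have some characteristic and one subject leaves early.
- N = 18: 9/18 = 50% becomes 8/17 = 47.1% or 9/17 = 52.9%.
- N = 20: 10/20 = 50% becomes 9/19 = 47.4% or 10/19 = 52.6%.

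**Chance that the rule omits anyone.** The protocol gives no dropout rate, so the proportion d leaving before day 30 is assumed, with subjects independent. Expected number omitted = N × d; chance of at least one = 1 − (1 − d)^N.

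| Assumed d | N = 18: expected | N = 18: chance of at least one | N = 20: expected | N = 20: chance of at least one |
|---|---|---|---|---|
| 5% | 0.9 | 60% | 1.0 | 64% |
| 10% | 1.8 | 85% | 2.0 | 88% |
| 20% | 3.6 | 98% | 4.0 | 99% |

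An exposure-based definition would omit no exposed subject at any d.

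**The case against.** The strongest reply is that little depends on this set. The only output explicitly tied to it is one descriptive table in a pilot of 18 to 20 subjects. Efficacy uses the other dataset, the SAE listing in 11.8 is not restricted to an analysis set, and no SAE rate is planned. All of that stands, and it limits the point. It does not remove it, because that table is the one that describes self-selected groups.

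A second reply is that 11.3 says completers are included without saying that others are excluded. That is literally true, so the exclusion is inferred. But no other route is given in the section that defines the sets. If others belong too, the set is undefined and still needs rewriting.

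A third reply is that 8.1 is simply incomplete. It lists no 90-day test either, which is a separate defect. As shown above, completing the schedule would not cure the retention condition.

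Three stronger readings are tempting but not supported:
- A reader might infer that an early leaver's SAE is lost because the subject is outside the safety set. Sections 9.4.1 and 11.8 do not tie reporting or listing to that set. The opposite reassurance is not safe either: read literally, 11.8.3 leaves a diet or exercise SAE unrecorded in early leavers and completers alike, contrary to the synopsis, 9.1 and 11.8.
- A reader might infer a large distortion of the baseline table. That needs several leavers who share a characteristic, and the protocol gives no basis for assuming so.
- A reader might infer that subjects are bled and then excluded, since 11.8.1 says "Physical Examination will be performed as a screening method to exclude cardiovascular pathologies" and 8.1 lists the examination after the blood draw. Section 8.1 does not say that its list is in time order. It confirms eligibility at the earlier meeting, and 8.2 mentions the examination alongside the first study visit.

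**Conclusion.** The point holds with a limited reach. Section 11.3 makes completion of an unscheduled assessment the only stated route into the safety set, and 11.4 passes that restriction to the baseline table. On the natural reading, an exposed subject who leaves before day 30 is missing from both and may still be in the analysis dataset. Each one costs 5.6% of 18 or 5.0% of 20. How many there would be is unknown, and the probabilities above rest on assumed dropout.

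The harm is to the safety population and to the description of self-selected groups at baseline. The 30-day rule alters neither the efficacy dataset nor any planned SAE rate. Whether SAEs from diet or exercise are captured is uncertain for a different reason, the wording of 11.8.3, and stays so until that section is reconciled with the synopsis, 9.1 and 11.8. The protocol fixes this definition itself, so an analysis plan that followed it would inherit the fault. It should be corrected before the data are analysed.

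**What to change.** - **11.3:** delete the 30-day condition and define the safety set as every subject who underwent any study procedure, from the blood draw onward, whether or not later assessments are completed.
- **11.4:** report demographic and baseline characteristics for all enrolled subjects, by treatment group because the groups are self-selected, with the denominator labelled.
- **11.8 and 11.8.3:** keep the listing unrestricted by analysis set, and reconcile the recording rule in 11.8.3 with 11.8, 9.1 and the synopsis.

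The cost is wording only. The downside is that the baseline table will include subjects without follow-up. Its denominator may differ from those of the safety set and the analysis dataset, so all three numbers should be shown.

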### **11.4 Demographics and Baseline Characteristics**

Demographic and baseline characteristics (age/age categories, sex, race, ethnicity, and baseline characteristics) will be analyzed using the safety analysis set. Summary statistics (n, mean, median, standard deviation, minimum, and maximum) will be reported. Information collected from the targeted medical history will be summarized in the same fashion as the other baseline characteristics.

### **11.5 Subject Accountability**

Subject compliance and accountability will be monitored with daily text transmission for the two month and then weekly communications through completion of the first six months in this study.

### **11.6 Study Treatment Usage and Compliance**

Subject compliance and accountability will be monitored with daily text transmission for two months and then weekly communications through completion of the first six months in this study.

### **11.7 Body Composition Testing**

Testing will be done in compliance the testing protocol supplied by the Electrical Impedance test guidelines.

## **11.8 Safety Analyses**

Any SAEs related or possibly related to study procedures will be listed.

### **11.8.1 Physical Examination and Vital Signs**

Physical Examination will be performed as a screening method to exclude cardiovascular pathologies such as arrhythmia or history of myocardial infarction before initiation of the subject's participation in this study.

### **11.8.2 Clinical Laboratory Tests**

Laboratory testing for food allergies will be conducted by the Cell Science System laboratory using the ALCAT method for all subjects.

### **11.8.3 Adverse Events**

Only SAEs related or possibly related to invasive study procedures will be recorded.

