## **3.1 Summary of Potential Risks**

This is a randomized, cross-over study that will not include and invasive treatments methods or pharmaceutical products. The risks in this study are as follows:

- Drawing blood for diagnostic testing by venipuncture is an invasive procedure that may occasionally be associated with adverse events such as pain, bleeding, syncope, or ecchymosis.
- The Aerobic-surge, 2-minute exercise bouts will have potential risks for injuries such as falls, scrapes, bruises, pulled connective tissue injuries, etc. However this risk is no greater than the risk in daily ambulation and activity.

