#### **5.1.2 Safety Endpoints**

Only serious adverse events (SAEs) associated with study procedures will be recorded.

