## TREATMENTS

The treatments will include the following:

- Elimination of foods showing any leukocyte reaction (tests all Ig reactions).
- Restructure of dietary schedule of eating to < 2 cups of food, five times each day.
- Participation in the 2-minute Aerobic-surge exercises (with HR  $\geq$  75% max HR) performed at home or work, five times per day.
- Consuming Natural foods five times a day, (included in the total 2 cup volume), 5/day.

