#### **8.4 Safety Assessments**

Any SAEs associated with study procedures will be recorded and reported.

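### Section 11.8.3 limits SAE recording to 'invasive' procedures, in effect the blood draw alone, while seven other sections cover all study procedures

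*Protocol*

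**What the plan says.** Section 11.8.3 (Adverse Events), in the statistics chapter, reads: "Only SAEs related or possibly related to invasive study procedures will be recorded".

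The word 'invasive' occurs in one other place, section 3.1 (Summary of Potential Risks). That section says of the study that it "will not include and invasive treatments methods or pharmaceutical products", and then lists the risks, beginning with: "Drawing blood for diagnostic testing by venipuncture is an invasive procedure". Its second listed risk is injury during the two-minute exercise bouts.

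Elsewhere the scope is wider:

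- The Synopsis, under Safety: "Serious Adverse Events associated with study procedures (ALCAT Blood draw, dietary changes and 2-minute exercise sessions) will be reported to the IRB".
- Section 5.1.2: "Only serious adverse events (SAEs) associated with study procedures will be recorded".
- Section 8.4: "Any SAEs associated with study procedures will be recorded and reported".
- Section 9.1 gives two examples of a procedure-related event, the blood draw and an Aerobic-surge injury, and then sets a recording rule for serious procedure-related events.
- Sections 9.3 and 9.4.1 (recording and IRB reporting) and 11.8 (listing) refer to study procedures with no mention of invasiveness.

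**The concern.** The rule in 11.8.3 begins with 'Only', so it excludes whatever it does not cover. A serious exercise injury must be recorded under sections 9.1 and 9.3 and must not be recorded under 11.8.3. Both cannot be followed. The disagreement also lies within one part of the protocol: 11.8 lists SAEs from any study procedure, and its own subsection restricts what is recorded for that listing.

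The restriction falls on the part of the intervention that distinguishes the two groups. Sections 7.2 and 11.8.2 give the allergen blood test to every subject. PAN-5, which contains the exercise, is the voluntary addition. Under 11.8.3 the one remaining source of recordable SAEs is common to both groups, so a serious harm from the added component would not appear. Section 12.4.5 allows the study to be stopped on the incidence and severity of adverse events, and that decision needs the events on record.

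**Working it through.** The plan gives no figure on this point, so the check compares texts and counts coverage.

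**Step 1. What does 'invasive' cover?** The four treatments in the Treatments section are allergen elimination, the portion schedule, the exercise ("Participation in the 2-minute Aerobic-surge exercises") and natural foods. Section 3.1 disclaims invasive treatment methods, so none of the four qualifies. Venipuncture is the only study procedure given the label. It is scheduled once, at the enrolment meeting in section 8.1: "Collection of blood through venipuncture for Food Allergen testing". Section 9.1 likewise speaks of a single draw.

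**Step 2. Scope of each section that says what is recorded, reported or listed.**

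| Protocol section | Governs | Scope |
|---|---|---|
| Synopsis, Safety | IRB reporting | Blood draw, diet and exercise, all named |
| 5.1.2 | Recording | Study procedures, no limit |
| 8.4 | Recording and reporting | Study procedures, no limit |
| 9.1 | Recording | Procedure-related; exercise injury given as an example |
| 9.3 | Recording | Study procedures, no limit |
| 9.4.1 | Recording; IRB report within 24 hours | Study procedures, no limit |
| 11.8 | Listing | Study procedures, no limit |
| 11.8.3 | Recording | Invasive study procedures only |

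Broad scope: 5 sections on recording (5.1.2, 8.4, 9.1, 9.3, 9.4.1) + 1 on IRB reporting (Synopsis) + 1 on listing (11.8) = 7. Narrow scope: 1. The severity grading under 9.3.2 and sections 9.3.3, 9.4.2 and 9.4.3 also use the unrestricted scope. Adding them gives 7 + 4 = 11, so seven is a minimum.

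**Step 3. Coverage under 11.8.3.**

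- Procedures named in the Synopsis: 1 of 3 (blood draw yes; dietary changes and exercise no).
- Treatments: 0 of 4.
- Risks listed in section 3.1: 1 of 2 (venipuncture yes; exercise bouts no).

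These three counts express the same fact, that only the blood draw is called invasive. They measure coverage, not risk.

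**The case against.** The best defence is that the loss is unlikely in practice. Chapter 9 governs what the site does: recording, causality, the 24-hour report to the IRB and follow-up are all unrestricted there. Staff would have to set aside that chapter, the safety endpoint and the safety assessment section in favour of one sentence in the statistics chapter. This stands as a limit on the seriousness of the point. It does not make the text consistent, and the sentence is the adverse-event rule in the chapter an analyst would consult.

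A second argument is that 'invasive study procedures' is nowhere defined, so reading it as the blood draw is an inference. That is true. The inference is sound, because no other study procedure carries the label and section 3.1 disclaims invasive treatments.

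A third is that the seven sections are not equally explicit. Only the Synopsis names dietary changes, and only the Synopsis and 9.1 name exercise. The other five support the point because they set no such limit. This is also true, but the two explicit sections are enough to establish the contradiction for exercise, and the Synopsis alone for diet.

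No efficacy analysis, sample size or test is affected.

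**Conclusion.** The contradiction is real and is in current text. Section 11.8.3, taken literally, removes SAEs from exercise and diet that the rest of the protocol requires to be recorded, reported or listed. Section 11.8.3 does not override the other sections, and whether anyone would follow it is unknown. The consequence is therefore conditional: if it is followed, serious events from two of the three procedures named in the Synopsis are lost, and a report of no SAEs could not be interpreted. The conclusion rests on one assumption, that 'invasive' carries the meaning given by its only other use, in section 3.1. The point should be corrected, but it does not threaten the efficacy results.

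**What to change.** Delete the word 'invasive' from section 11.8.3. The sentence then has the same scope as the Synopsis and sections 5.1.2, 8.4, 9.1, 9.3, 9.4.1 and 11.8, and nothing else needs to change. The cost is one word in a protocol amendment, with no new visit, contact or data field. If the change is made after enrolment has begun, the sponsor should also confirm that no exercise- or diet-related SAE was left unrecorded under the narrower wording.

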### **11.8.4 Other Statistical Issues**

Deviations from the statistical plan, along with the reasons for the deviations, will be described in protocol amendments, the complete statistical plan, the clinical study report, or any combination of these, as appropriate.

### **11.8.5 Significance Levels**

Differences beyond 0.05 will be considered significant.

### **11.8.6 Missing or Invalid Data**

N/A

## **11.9 Interim Analysis**

N/A

## **12 SPECIAL REQUIREMENTS AND PROCEDURES**

This protocol was designed and will be conducted, recorded, and reported in compliance with the International Conference on Harmonization/Good Clinical Practice guideline. These requirements are stated in the International Conference on Harmonization Guideline Topic E6 entitled “Guideline for Good Clinical Practice.”

### **12.1 Institutional and Ethics Review**

This protocol, informed consent form, participant information sheet, and any proposed advertising material will be submitted to an appropriate ethics committee, applicable regulatory authorities, and host institution(s) for written approval (where applicable). These documents will also be submitted to and approved by the above parties for all substantial amendments to the original approved documents (where applicable). Documentation of any applicable approval(s) and the approved consent form must be received by the Sponsor or its designee prior to enrollment of patients.

